4.2 Switching of treatments

At the discretion of the investigator, patients can switch from deferasirox DT to deferasirox FCT at any time during Period 1 of the Core phase, and vice versa, from deferasirox FCT to deferasirox DT at any time during Period 2 of the Core phase.

This change and the rationale of the switch must be recorded in the CRF. Also the investigator must provide the preference questionnaire to the patient at the immediate next visit and then keep following the schedule of questionnaires pre-planned on [Table 7-1](#) and [Table 7-2](#) (for example; if the investigator decides to switch from deferasirox DT to deferasirox FCT at Week 12, the preference questionnaire must be provided to the patient on the next visit, Week 16, and the rest of the preference questionnaires as per regular schedule: Week 24, Week 28 and Week 48). Please refer to [14 Appendices](#) for further information on preference questionnaire completion.

The investigator can decide in the best interest of the patient to switch from one formulation to the other with the agreement of the patient if an adverse event (*defined as the appearance of (or worsening of any pre-existing) undesirable sign(s), symptom(s), or medical condition(s) that occur after patient's signed informed consent has been obtained*) grade ≥ 2 (GI symptoms, skin rash, laboratory abnormalities) occurred with deferasirox DT or deferasirox FCT.

Re-switching treatments is not allowed within each period in this study, which means that a patient cannot switch from Deferasirox DT to Deferasirox FCT and the switch back to Deferasirox DT, and viceversa (Deferasirox FCT to Deferasirox DT, and then back to Deferasirox FCT).

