10.5.3.2 Adverse events (AEs)

Summary tables for adverse events (AEs) will include only AEs that started or worsened during the on-treatment period, the *treatment-emergent* AEs. The AEs will be summarized separately and compared for two treatment groups FCT (Week 25 to 48) and DT (Baseline Day 1 to Week 24).

The incidence of treatment-emergent adverse events (new or worsening from baseline) will be summarized by system organ class and or preferred term, severity (based on mild, moderate, severe, life threatening, death), type of adverse event, relation to study treatment. If a patient reported more than one AE with the same preferred term, the AE with the greatest severity will be presented. If a patient reported more than one AE within the same primary system organ class, the patient will be counted only once with the greatest severity at the system organ class level, where applicable.

Serious adverse events, non-serious adverse events and adverse events of special interest (AESI) which are specific gastrointestinal events during the on-treatment period will be tabulated.

Separate summaries will be provided for death, SAE, other significant AEs leading to discontinuation and AEs leading to dose adjustment (including study treatment discontinuation).

As appropriate, the incidence of AEs will be presented per 100 patient years of exposure.

All AEs, deaths and serious adverse events (including those from the pre and post-treatment periods) will be listed and those collected during the pre-treatment and post-treatment period will be flagged.

A graphical display of relative frequencies within system organ classes and relative risks, as appropriate, may be presented is required.

For AEs of special interest, time-to-event analysis will be performed, as appropriate and as described in the statistical analysis plan. Results will be tabulated and the Kaplan-Meier estimates for the cumulative rate will be plotted.

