| To evaluate the overall safety of deferasirox FCT compared with deferasirox DT  | Overall safety, as measured by frequency and severity of adverse events and changes in laboratory values of interest during deferasirox FCT (Week 25 to 48) compared with deferasirox DT (Baseline day 1 to Week 24) |
| To evaluate efficacy of deferasirox ( both DT and FCT) in decreasing serum ferritin levels  | Absolute and relative change from baseline ( Day 1) in serum ferritin on monthly basis   |

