## 2.2 Analysis sets

The following analysis sets will be used in this study.

**Enrolled Set:** The Enrolled Set comprises all patients enrolled in this study. Patients who discontinued from the study due to ineligibility immediately after Visit 2 are not considered as enrolled.

**Full Analysis Set (FAS):** The Full Analysis Set comprises all patients to whom study treatment has been assigned and who received at least one dose of each study treatment (DT and FCT). Patients will be analyzed according to the treatment they have been assigned to.

**Safety Set (SAF):** The Safety Set includes all patients who received at least one dose of either study treatment (DT or FCT), and at least one safety assessment on or after Day 1.

Patients will be analyzed according to the study treatment received, where treatment received is defined as the assigned treatment if the patient took at least one dose of that treatment or the first treatment received if the assigned treatment was never received.

**Per-Protocol Set (PPS):** The Per-Protocol Set consists of a subset of the patients in FAS who are compliant with requirements of the clinical study protocol (CSP) without any major protocol deviation.

Any major protocol deviation will lead to exclusion of patients from PPS. The list of PDs is defined in [Section 5.5](#).

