## 2.4 Treatments (study treatment, rescue medication, concomitant therapies, compliance)

### 2.4.1 Study treatment / compliance

#### Study treatment

The following variables will be summarized descriptively for each study treatment period based on the Safety Set. Summaries will be presented overall and by age groups and also on prior intake of iron chelation status (naïve or pre-treated) and thalassemia transfusion status (transfusion or non-transfusion), separately for Core and Extension phases.

- The number of medications (pills) received for each dosing regimen
- The duration of exposure (in weeks) and in categories (< 4 weeks, 4-< 12 weeks, 12-< 24 weeks, ≥ 24 weeks)
- Average planned (mg/kg/day) and average actual daily dose (mg/kg/day)
- Cumulative planned (mg/kg) and cumulative total actual dose (mg/kg)
- Percentage of planned dose taken
- Dose intensity (computed as the ratio of actual cumulative dose received and actual duration of exposure)
- Relative dose intensity (computed as the ratio of dose intensity and planned dose intensity)

The number of patients with dose adjustments (increase, reductions, interruption, or permanent discontinuation) and the reasons of change and interruption will be summarized for all patients and by treatment group. Dose adjustments for auditory, hypersensitivity reactions and cytopenias will also be summarized.

The number of patients with ‘switching’ (this is a switch outside the normal switch at the end of Week 24) from one treatment to another at any treatment period along with the reasons of switching will also be summarized. In case of switching within each treatment period, duration of exposure will be calculated accordingly as described below.

The duration of exposure is defined as the number of weeks between the start and end of study medication. The exposure calculation will be based on the actual date of switch from one treatment to another. The end of study medication day is the last day with a non-zero actual dose of study medication as recorded on the drug administration pages.

The average daily dose (planned or actual, in mg/kg) is calculated as the mean dose over all days between first and last dose, including interim days with zero dose (interruptions). The final daily dose is recorded as the last non-zero dose. The cumulative dose is calculated as the sum over the daily doses of all days between first and last dose. The current weight is used when calculating the actual daily dose.

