**Compliance using pill count**

Compliance is measured by pill/tablet count based on amount of medication dispensed, returned and reported as lost/wasted by the patient or caregiver. Compliance will be calculated for each treatment (FCT: Week 25- Week 48, DT: Baseline day 1 – Week 24) as the ratio of total count consumed to total count prescribed, where total count consumed is derived from cumulative dispensed, returned and lost/wasted counts and total count prescribed is the cumulative prescribed count.

The prescribed count corresponds to the count prescribed by the investigator for a period that the patient should have taken during this period. For each strength (125 mg, 250 mg and 500 mg tablets for Deferasirox DT; 90 mg, 180 mg and 360 mg tablets for Deferasirox FCT), the prescribed count for a period is calculated from the daily prescribed count at the beginning of this period multiplied by the duration (days) of this period. The daily prescribed count is the sum of counts prescribed per strength. The duration of a period will be calculated as (end date of the period) – (start date of the period) + 1. The following period duration calculation will exclude the start day. The total count prescribed is the sum of counts prescribed over all periods.

If a patient does not return the study drug, the compliance will not be calculated.

Analysis of covariance (ANCOVA) will be performed for comparison between both treatment groups (FCT and DT). The ANCOVA model for compliance endpoint will include treatment group and age group (2 to < 6 years, 6 to < 10 years, 10 to < 18 years, and  $\geq$  18 years) and thalassemia transfusion dependence (TDT and NTDT) as factors. Least squares estimates, 95% CI and p-value will be presented for each treatment and difference between treatments.

Summary statistics of number of pills (and percentages) will also be presented overall and by treatment and subgroups.

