### 2.8.1 Adverse events (AEs)

Summary tables for AEs will include only AEs that started or worsened during the on-treatment period, the *treatment-emergent* AEs.

The incidence of treatment-emergent AEs (new or worsening from baseline) will be summarized by system organ class and or preferred term, severity (mild, moderate, severe), type of adverse event, relation to study treatment. If a patient reported more than one AE with the same preferred term, the AE with the greatest severity will be presented. If a patient reported more than one AE within the same primary system organ class, the patient will be counted only once with the greatest severity at the system organ class level, where applicable.

Severity is captured in CRF as per CTCAE V 4.03 grades. The mapping from CTCAE to severity grade is given below:

- Grade 1=Mild
- Grade 2= Moderate

- Grade 3= Severe
- Grade 4 = Life- threatening
- Grade 5= Death related to AE

In this study the grade  $\geq 3$  will be considered as severe.

As appropriate, the incidence of AEs will be presented per 100 patient years of exposure.

The following adverse event summaries will be produced by treatment for Safety Set:

- Adverse events (overall and severe), regardless of study drug relationship by primary system organ class and preferred term
- Adverse events, regardless of study drug relationship by primary system organ class and preferred term and severity
- Adverse events (overall and severe), with suspected study drug relationship by primary system organ class and by preferred term
- Serious adverse events (overall and severe), regardless of study drug relationship, by primary system organ class and preferred term
- Adverse events leading to study drug discontinuation (overall and severe), regardless of study drug relationship, by primary system organ class and preferred term
- Adverse events requiring dose adjustment or study-drug interruption (overall and severe), regardless of study drug relationship, by primary system organ class and preferred term
- Adverse events requiring additional therapy (overall and severe), regardless of study drug relationship, by primary system organ class and preferred term

The incidences listed above will additionally be summarized by preferred term.

- Deaths by primary system organ class and preferred term.
- Non-serious adverse events, regardless of study drug relationship, by primary system organ class and preferred term (for clinicaltrials.gov purpose)

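### DT-versus-FCT safety and compliance comparisons are defined by study week while exposure follows the actual switch date, and the SAP does not say how data after an unplanned formulation switch are attributed

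*Protocol*

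**What the plan says.** Protocol 4.2 states that, at the investigator's discretion, "patients can switch from deferasirox DT to deferasirox FCT at any time during Period 1 of the Core phase, and vice versa" in Period 2. Re-switching within a period is not allowed, so a patient who switches and stays on treatment remains on the other formulation until that period ends. SAP 5.5 (deviations S05 and S06) exempts these switchers from exclusion, so their data stay in the analysis.

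Outcomes are grouped by study week:
- Adverse events: Protocol 10.5.3.2 has them "compared for two treatment groups FCT (Week 25 to 48) and DT (Baseline Day 1 to Week 24". Protocol 10.5.3.3 uses the same windows for laboratory values.
- Safety endpoint: SAP Table 1.2.1 compares adverse events and laboratory changes "during deferasirox FCT (Week 25 to 48) compared with deferasirox DT (Baseline day 1 to Week 24".
- Compliance: SAP 2.7.2 says "Compliance will be calculated for each treatment (FCT: Week 25- Week 48, DT: Baseline day 1" to Week 24.

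Exposure is grouped by formulation taken. SAP 2.4.1, like Protocol 10.3.1, says "The exposure calculation will be based on the actual date of switch from one treatment to another".

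SAP 2.8.1 adds: "As appropriate, the incidence of AEs will be presented per 100 patient years of exposure". It calls for adverse event tables by treatment, without week windows or a rule for switchers. The Safety Set definition in SAP 2.2 classifies patients by treatment received, where "treatment received is defined as the assigned treatment if the patient took at least one dose of that treatment".

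**The concern.** Take a patient who moves from DT to FCT at Week 12 and has a new adverse event at Week 20. Under the week windows that event belongs to DT, although the patient had been on FCT for eight weeks. Laboratory values from Weeks 12 to 24 go the same way. FCT tablets taken in those weeks are either counted in the DT compliance window or dropped; the plan does not say which. The event that prompts a switch is attributed correctly. The problem is what follows it within the same period.

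If the switch-date exposure is used as the denominator for rates per 100 patient-years, a second problem arises. The numerator is defined by week and the denominator by formulation, so the rate describes neither.

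Comparing FCT with DT on safety and on compliance are stated secondary objectives. Two programmers following the same plan could produce different tables. Grade 2 or higher adverse events are a named reason for switching (Protocol 4.2 and 6.2.2), so the affected person-time need not come from typical patients.

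**Working it through.** **The plan's own figure.** The documents give no adverse event rate, switch rate or safety precision to reproduce. The only computed figure is the sample size. With 70% discordant and a 20-point difference, (1.960 + 0.842)² × (0.70 − 0.04)/0.04 = 129.5, so 130; and 130/0.90 = 144.4, so 145. That agrees with the plan. It is used here only for N = 145.

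**Assumptions for the illustration (not in the documents).** All 145 complete 48 weeks; k patients move from DT to FCT at Week 12; none move back; the true event rate is constant and equal on both formulations.

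**Week-defined events over formulation-defined person-time.** Each period holds 145 × 24 = 3,480 patient-weeks and, with equal rates, the same expected number of events. Actual exposure is 3,480 − 12k weeks on DT and 3,480 + 12k weeks on FCT. The apparent FCT/DT ratio is therefore (3,480 − 12k)/(3,480 + 12k).

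| k (share of 145) | DT weeks | FCT weeks | DT rate × | FCT rate × | Apparent ratio |
|---|---|---|---|---|---|
| 7 (4.8%) | 3,396 | 3,564 | 1.025 | 0.976 | 0.95 |
| 15 (10.3%) | 3,300 | 3,660 | 1.055 | 0.951 | 0.90 |
| 22 (15.2%) | 3,216 | 3,744 | 1.082 | 0.929 | 0.86 |

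Across one-way switching of 5% to 30% at Week 4, 12 or 20, the ratio runs from 0.98 (5% at Week 20) to 0.60 (30% at Week 4).

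**Symmetric switching.** If 15 others move from FCT to DT at Week 36, exposure returns to 3,480 weeks each and the ratio is 1.00.

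**A true ratio of 0.70, with exactly 10% moving to FCT at Week 12.** Per patient, DT-window events are 22.8 + 0.7 × 1.2 = 23.64 and FCT-window events are 0.7 × 24 = 16.8 (DT rate set to 1).
- Mixed rule: (16.8/25.2)/(23.64/22.8) = 0.64.
- Weeks on both sides: 16.8/23.64 = 0.71.
- Switching in both directions: (0.7 × 22.8 + 1.2)/23.64 = 0.73, a dilution.

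**Would as-taken attribution alone suffice?** Keep k = 15 and equally safe formulations, but give switchers twice the event rate on both. The 130 non-switchers contribute 130 × 24 = 3,120 events per period and the switchers 15 × 24 × 2 = 720.
- Mixed rule: (3,840/3,660)/(3,840/3,300) = 0.90, the same as before.
- Crude as-taken: DT (3,120 + 360)/3,300 = 1.055; FCT (3,120 + 1,080)/3,660 = 1.148; ratio 1.09. At three times the rate it is 1.17.
- Weeks on both sides: 3,840/3,480 in each period; ratio 1.00.
- Non-switchers only: 3,120/3,120; ratio 1.00. Within switchers: (1,080/540)/(360/180) = 1.00.

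Matching the two sides removes the mismatch. Crude as-taken pooling then brings in confounding by switch status, which stratifying removes in this example.

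**The case against.** The strongest reply is that the plan is under-specified rather than demonstrably wrong.

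- The switch-date sentence defines exposure for the study-treatment summaries. Nothing says it is the denominator for rates per 100 patient-years, and those are planned only as appropriate.
- The main adverse event tables are patient counts and percentages, to which the 0.90 ratio does not apply.
- SAP 2.8.1 says only that tables are by treatment, and Protocol 10 allows patients to appear in more than one treatment group. Both fit as-taken attribution.
- The Safety Set rule classifies patients. Since every patient is meant to take both formulations, it cannot settle where an event belongs.
- SAP 2.7.2 counts tablets by strength, so DT and FCT tablets can be told apart.

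All of this stands as a limit on size. It does not remove the gap. The SAP's Introduction adopts the protocol's methods unless it says otherwise, and SAP 4 declares no change from the protocol's analyses. The week windows of Protocol 10.5.3.2 and 10.5.3.3 therefore still apply, and SAP Table 1.2.1 repeats them. Counts, percentages and the FCT-minus-DT risk difference escape the rate mismatch but not the misattribution.

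A reader might infer that switchers are handled separately only in the primary analysis. The documents do not support that. Protocol 10.5.3.5 plans supportive analyses for the secondary objectives similar to the primary ones, which include a split by switching. Its cross-reference to section 4.4 presumably means 10.4.4. Preference and other questionnaire data after a switch also get their own summaries. What is missing is any SAP text that carries the split into safety or compliance.

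A planned-period comparison is also a legitimate choice. In the calculations above, weeks on both sides give 1.00 or close to the true 0.70. The objection is therefore right that as-taken attribution should not simply replace it.

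**Conclusion.** The point holds as an unresolved attribution rule in a secondary comparison. Switching is allowed in both core periods, outcomes are grouped by week and exposure by switch date, and no text assigns an adverse event, laboratory value or tablet count after a switch to the formulation being taken. Read literally, such data fall under the formulation the patient has left, and a rate per patient-year may mix the two rules.

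The size is conditional. An apparent ratio of 0.90 needs about 10% one-way switching at Week 12, equal true rates and the mixed denominator. Fewer, later or two-way switches shrink it or cancel it.

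A reader might go further and infer that the adverse event rates will be biased in favour of FCT, that every switch reflects poor tolerability, or that the mismatch grows if switchers are prone to adverse events. The documents support none of these. They give no switch rate or direction. Protocol 4.2 allows switching at the investigator's discretion, and Protocol 7.1.3.1 also contemplates it for an unsatisfactory effect. The mixed ratio stays at 0.90 when switchers have twice the event rate.

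SAP 2.7.2 plans no formal hypothesis tests for secondary endpoints, and the primary endpoint and sample size are untouched. This should be fixed, but it does not threaten the trial's main conclusion.

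**What to change.** In SAP 2.7.2, 2.8.1 and 2.8.3, require that every DT-versus-FCT table use one attribution rule for both numerator and denominator, and name the rule in the table title. Then specify:

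1. A planned-period comparison (Day 1 to Week 24 against Week 25 to 48) with planned-period person-time.
2. An as-taken comparison that assigns each adverse event onset, laboratory value, tablet count (by strength) and day of person-time to the formulation taken on that date, using the recorded switch dates. For laboratory changes, state which value is the FCT baseline for a patient who switched before Week 25, because SAP 2.8.3 sets baselines by period.
3. Both comparisons in patients who did not switch, or stratified by switch status, because a crude as-taken pool is confounded if switchers have higher event rates. This would also put Protocol 10.5.3.5 into effect.

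The cost is a few sentences in the SAP, one derived variable (formulation at date) and an extra set of tables. No new data are needed: switches are recorded in the CRF and dosing start and end dates in the dose administration record. DT and FCT exposure will differ in length between patients in the as-taken tables.

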10.5.3.3 Laboratory abnormalities

The summary of laboratory evaluations will be presented for different groups of laboratory tests (hematology, serum chemistry, serum ferritin, serum creatinine, and urinalysis). Descriptive summary statistics for the change from baseline to each study visit will be presented. These descriptive summaries will be presented by test group, laboratory test and treatment group. Change from baseline will only be summarized for patients with both baseline and post-baseline. The laboratory evaluations will be summarized separately and compared for two treatment groups FCT (Week 25 to 48) and DT (Baseline Day 1 to Week 24).

For each parameter, the maximum change from baseline within each study period will be evaluated analogously.

In addition, shift tables will be provided for all parameters to compare a patient's baseline laboratory evaluation relative to the visit's observed value. For the shift tables, the normal laboratory ranges will be used to evaluate whether a particular laboratory test value was normal, low, or high for each visit value relative to whether or not the baseline value was normal, low, or high. These summaries will be presented by laboratory test and treatment group. Shifts will be presented by visit as well as for most extreme values post-baseline.

Grading of laboratory values will be assigned programmatically as per NCI Common Terminology Criteria for Adverse Events (CTCAE) version 4.3. The calculation of CTCAE grades will be based on the observed laboratory values only, clinical assessments will not be taken into account.

CTCAE Grade 0 will be assigned for all non-missing values not graded as 1 or higher. Grade 5 will not be used.

For laboratory tests where grades are not defined by CTCAE v4.3, results will be categorized as low/normal/high based on laboratory normal ranges.

The following summaries will be generated separately for hematology, and biochemistry tests:

- Listing of all laboratory data with values flagged to show the corresponding CTCAE v4.3 grades if applicable and the classifications relative to the laboratory normal ranges ([Table 10-1](#))
- For laboratory tests where grades are defined by CTCAE v4.3
- Worst post-baseline CTCAE grade (regardless of the baseline status). Each patient will be counted only once for the worst grade observed post-baseline.
- Shift tables using CTCAE v4.3 grades to compare baseline to the worst on-treatment value

For laboratory tests where grades are not defined by CTCAE v4.3,

- Shift tables using the low/normal/high/ (low and high)

- Classification to compare baseline to the worst on-treatment value.

Apart from the above laboratories summaries, summaries of Hepatitis Viral tests will also be performed.

Table 10-1 Definition of notable/extended ranges for laboratory test

Laboratory test	Criteria for notable ranges
Platelet count	< 100 x 10 ⁹ /L (extended range <50×10 ⁹ /L)
Absolute neutrophils	< 1.5 x 10 ⁹ /L (extended range <0.5×10 ⁹ /L)
Serum creatinine	> 33% increase from baseline and > ULN at two consecutive measurements at least 7 days apart
Creatinine clearance*	<60 mL/min at two consecutive measurements at least 7 days apart (extended range <40 mL/min at two consecutive measurements at least 7 days apart)
Urinary protein/urinary creatinine ratio	≥ 1.0 (mg/mg) at two consecutive measurements at least 7 days apart
ALT and AST	>5 x ULN and >2 x baseline value (extended range >10×ULN and >2×baseline value)

* Creatinine clearance will be estimated using the Schwartz formula

